9.5 Outcomes

Please refer to Section 9.1. Analysis and outcomes will be reviewed by PI, Co-Is, and consultants as needed.

9.5.1 Primary Outcome

The primary outcome is pain-related fear (adolescent and parent). This will be measured through the Fear of Pain Questionnaire (FOPQ-C, FOPQ-P) measure collected at Baseline, treatment study Discharge, and 3 and 6-month post-discharge follow-up time points. The Photographs of Daily Activities (PHODA-YE) will also be used to measure pain-related fear outcomes at Baseline and treatment study Discharge.

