3. STUDY DESIGN

This study employs a two-group randomized, controlled design to test GET Living, for adolescents with chronic musculoskeletal pain and elevated pain-related fear (**Figure 3**). **Primary outcome** is pain-related fear avoidance (adolescent, parent). **Secondary outcome** is disability. Additional outcomes are parent responses to pain and pain acceptance. Exploratory: adolescent biomechanics and physical activity.

[figure not shown]

Figure 3. Study Design. a) Eligibility Screening: musculoskeletal pain patients (ages 8-18; pain > 3 months) at Stanford Children's Health (SCH); b) Baseline Visit (BAS): Consent/Accent, Baseline Assessment: SR, motion analysis; Baseline Daily Diary: DD and actigraphy; c) Randomization: randomization to treatment group; d) GET Living and TPM begin: DD and actigraphy ongoing; e) Discharge Assessment: SR, motion analysis; f) 3-month Follow-Up: SR, 7-day DD, g) 6-month Follow-Up: SR, 7-day DD. Note. **DD**=daily diary; **SR**=self-report; **W**=week.

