Aim 1 Analysis Plan. GET Living vs. TPM. Linear mixed effects models will be used to compare GET Living to TPM. The outcome of interest for H_{1a} will be FOPQ-C and PFOPOQ total scores. For H_{1b}, outcomes are FDI and ARCS-Protect scores. Exploratory endpoints. Daily Diary (DD): We will use a randomization test (<https://tamalkd.shinyapps.io/scda/>)⁵³ to assess the difference between baseline (BAS) to discharge (END) and BAS to 3 and 6-month follow-up (FU)^{21,54}. We will also examine at what point during treatment significant improvements occur using delayed effect lags (one effect equals 1 day) until p-value 0.05 is reached. Actigraphy: Actilife software will be used to extract data and calculate mean and peak daily activity. Published data reduction methods will be used⁴³. We will model physical activity (mean, peak) at two time points using mixed 2 (time) x 2 (group) ANOVAs. Rate of change in physical activity from BAS to END will also be examined using DD method. Biomechanical assessment: Full body joint kinematic (motion) and kinetic (force) data will be collected with a 20-camera Vicon system (Centennial, CO, USA) with 5 integrated force plates (Bertec; AMTI). Markers will be placed on each participant according to the 3D Plug In Gait model (Vicon) with data recorded and processed in Nexus 2.6.1. Participants will walk, complete the Star excursion balance test and drop jump task^{37,41}. Biomechanical variables (stride length; peak hip and knee extensor moments; peak ankle plantarflexor moment; Star excursion balance score) will be extracted using Event Analyser (Vicon) for error free data reduction. We will model biomechanical variables using mixed 2 (time) x 2 (group) ANOVAs. We will also examine treatment response correlates: age, pain, gender, diagnosis, and readiness to change.

Aim 2: To characterize feasibility of GET Living to inform implementation of a large multi-site RCT.

Hypotheses: GET Living participants will have (1) high treatment satisfaction ratings (mean score ≥ 40 of 60; reflective of satisfied or very satisfied); *Secondary:* (2) $\geq 80\%$ sessions completed on-schedule, $\leq 20\%$ attrition rate, $\geq 80\%$ adolescent and parent daily diary adherence; *Exploratory:* (3) fewer health care costs at 3 and 6-month follow-up compared to TPM.

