9.2 Sample Size and Randomization

We chose the largest feasible study size to obtain as precise estimates as possible of improvement in adolescent disability while ensuring adequate power for the treatment difference in the improvement in adolescent pain-related fear. This gave us a starting total sample size of 74 (37 in each arm). Based on pilot data, we expect roughly 19% attrition during treatment to a total of 60 and further attrition to 58 at end of follow-up.

Power calculations were first performed using the simplified approach of paired t-tests for the change from baseline to 3 and 6-months on those with 3 and 6-months data. For this approach, we used means and standard deviations of observed changes in pilot data. We then simulated data from our analytic model using the standard deviations at each time point and standard deviations of change to calculate correlation and hence the random effect and error variances. The mixed models simulation allowed us to use more data and yielded slightly higher power estimates.

Primary Outcome: In our primary power calculation, we assumed that the improvement in adolescent pain-related fear at 3 and 6-months would be 22.4 in GET Living and 5 in TPM, a difference of 17.4, with a standard deviation for change of 21. Under this scenario we will have power of 87% with 58 (29 in each arm) at end of study. Under more conservative assumptions, we still have power of 80% with only 52 at the end of study and a treatment difference of 16.6. With a smaller standard deviation of 18.9, we will have power of 80% with 50 at end of study and a treatment difference of 15.4.

Other Outcomes: For parent pain-related fear, our estimated treatment difference at 3 and 6-months is 13 with an estimated standard deviation for change of 8.5. This would give us power close to 100% for 58 at end of study and we would still have 90% power with a treatment difference of only 8 and only 50 left at end of study.

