9.6 Data Analyses

Our statistician, [name], will conduct analyses. Linear mixed effects models will be used for Aim 1. We chose the largest feasible study size to obtain as precise estimates as possible of treatment difference in our primary outcome, adolescent pain-related fear. With a starting sample of 74 (37/37), we expect 58 at follow-up (18% discharge attrition, 5% at 3 and 6-month follow-up). Using GET Living pilot data (see Table 2), we used a mixed model simulation using the standard deviations at each time point and standard deviations of change to calculate correlation and hence the random effect and error variances. In our primary power calculation, we assumed that the improvement in adolescent pain-related fear at 3 and 6-months would be 22.4 in GET Living and 5 in TPM¹⁹, a difference of 17.4, with a standard deviation for change of 21. Under this scenario we will have 87% power with 58 (29 in each arm) at study end. Under more conservative assumptions, we still have power of 80% with only 52 at the end of study and a treatment difference

of 16.6. With a smaller standard deviation of 18.9, we will have power of 80% with 50 at end of study and a treatment difference of 15.4.

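### The plan defines the primary outcome in two ways, adolescent plus parent fear or adolescent fear alone, and gives no rule for success or for the interim stop

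*Combined protocol and SAP*

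**What the plan says.** Adolescent and parent fear together:

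- Section 3: the primary outcome "is pain-related fear avoidance (adolescent, parent".
- Section 9.5.1: "The primary outcome is pain-related fear (adolescent and parent". On instruments: "This will be measured through the Fear of Pain Questionnaire (FOPQ-C, FOPQ-P) measure". It then adds a further measure: "The Photographs of Daily Activities (PHODA-YE) will also be used to measure pain-related fear outcomes at Baseline and treatment study Discharge".
- Table 6 puts FOPQ-C, the parent scale and PHODA-YE in the primary outcome row.
- The first Aim 1a hypothesis, under the Primary Objective in section 1.1 and again in section 9.1, names both reporters. The section 9.1 analysis plan models "FOPQ-C and PFOPOQ total scores" for that hypothesis. It does not call them primary and does not mention PHODA-YE.

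Adolescent fear alone:

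- Section 9.2: "Primary Outcome: In our primary power calculation, we assumed that the improvement in adolescent pain-related fear". Parent fear comes later, in the paragraph on other outcomes: "For parent pain-related fear, our estimated treatment difference at 3 and 6-months is 13 with an estimated standard deviation for change of 8.5".
- Section 9.6 refers to the "treatment difference in our primary outcome, adolescent pain-related fear".

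Section 9.4 sets significance levels of 0.0054 (interim) and 0.0492 (final), and a futility stop at conditional power below 10%. It names no outcome. No section gives a hierarchy, an alpha split or a both/either rule for the two questionnaires. The parent scale is called FOPQ-P in section 9.5.1, PFOPQ in Table 6 and PFOPOQ in section 9.1.

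**The concern.** The trial is meant to decide whether a large multi-site trial is justified, and it can stop early for efficacy or futility. Both decisions need one known test. The two candidate measures are not expected to behave alike. In the pilot (section 2.2, Table 1) the effect size was 0.71 for parent fear and 0.36 for adolescent fear, and the planned power differs in the same direction. One set of interim data could therefore stop the trial on one measure and continue it on the other. If the rule is not fixed beforehand, the choice could be made after the data are seen.

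**Working it through.** **Inputs.** Sections 9.2 and 9.6: FOPQ-C difference 17.4, SD of change 21, 29 per arm, stated power 87%. Section 9.2: parent fear difference 13, SD 8.5, stated power close to 100%; also 90% at a difference of 8 with 50 in total. The level of 0.05 is stated in section 9.2 for the disability simulation; two-sided testing is assumed. The correlations between measures are assumptions, because the documents give none.

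**Step 1: reproduce the plan's power.** Two-sample t-test on change, with noncentrality = difference / (SD × √(2/n)) and n per arm.

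- FOPQ-C, n = 29: 17.4 / (21 × √(2/29)) = 3.155, power 87.3% (stated 87%).
- FOPQ-C, n = 26: 16.6 / (21 × √(2/26)) = 2.850, power 79.8% (stated 80%).
- FOPQ-C, n = 25, SD 18.9: 15.4 / (18.9 × √(2/25)) = 2.881, power 80.6% (stated 80%).
- Parent fear, n = 29: 13 / (8.5 × √(2/29)) = 5.824, power 99.99% (stated close to 100%).
- Parent fear, n = 25: 8 / (8.5 × √(2/25)) = 3.328, power 90.3% (stated 90%).

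The power figures are sound. The 87% is the power for adolescent fear alone.

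**Step 2: apply the three rules that the text leaves open.**

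- *FOPQ-C alone.* One test and no inflation. Power is 87.3% at 0.05 and 87.2% at 0.0492.
- *Both required.* No alpha split is needed and there is no inflation. Joint power at 29 per arm is 0.873 × 0.9999 = 0.873, assuming independence. Under the plan's own pessimistic values with 50 remaining, it is 0.806 × 0.903 = 0.728.
- *Either suffices, each at 0.05.* False-positive rate 1 − 0.95² = 9.75% if independent, 9.1% at correlation 0.5 and 8.4% at 0.7. At the final level of 0.0492 it is 1 − 0.9508² = 9.6% if independent, and 8.9% and 8.2% at those correlations. A simulation of both looks (2 million runs, interim at half the information) gives about 10.0%, 9.3% and 8.6%. The same simulation gives about 5.1% for one outcome, so nearly all the excess comes from the second test.

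**Step 3: parent-only success under the either-suffices rule.**

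- No adolescent effect, planned parent effect of 13: 1 − (1 − 0.9999) × 0.95, about 99.99% chance of a positive trial.
- No adolescent effect, parent effect of 8 with 50 remaining: 1 − 0.0967 × 0.95 = 90.8%.
- All planned effects true: parent significant and child not, (1 − 0.873) × 0.9999 = 12.7%, assuming independence.

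**Step 4: PHODA-YE.** If it also counted as a primary test on an either-suffices basis, three tests at 0.05 would give 1 − 0.95³ = 14.3% if independent and 12.5% at correlation 0.5. This is a further condition, since section 9.1 does not list PHODA-YE among the outcomes modelled for this hypothesis.

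**The case against.** A reader might infer that section 9.5.1 as written lets a parent-only result meet the primary outcome, and that the error rate is therefore about double. The documents do not support that. Sections 9.5.1 and 9.1 join the two measures with the word and, which fits a both-required rule at least as well; a parent-only result would then fail. It would also fail if sections 9.2 and 9.6 govern. No passage says that either one suffices.

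A reader might also regard the parent score as the weaker measure because parents are unblinded and are treated in GET Living. Section 6.2.3 leaves the patients unblinded too, and FOPQ-C is their own report. TPM also includes three parent-only sessions (section 5.1). Neither fact separates the reporters. Keeping parent fear as primary is defensible: the Précis defines a participant as a child with at least one parent, and section 2.1 gives parental fear equal importance.

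The three names for the parent scale look editorial; nothing suggests that more than one scale is meant. Finally, the trial calls itself exploratory.

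These points limit the consequence but do not remove the contradiction. An exploratory label does not remove the need for a rule when the plan sets significance levels and an efficacy stop.

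**Conclusion.** The concern holds as an inconsistency with a missing decision rule. The sections disagree on the primary outcome, and nothing says which measure or combination decides success or the interim stop. This is more than a labelling matter, because planned power is 87% for one measure and close to 100% for the other.

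The false-positive rate of about 9-10% (9.75% if independent, 9.1% at an assumed correlation of 0.5) and the possibility of a parent-only positive trial hold only under an either-suffices reading, which the text neither states nor excludes. Under the other two readings this source adds no inflation. The figures assume two-sided tests and, where stated, independence.

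**What to change.** The text is wrong as written, because its sections contradict each other. Put one definition and one success rule in sections 1.1, 3, 9.1, 9.2, 9.5.1, 9.6 and Table 6, before the interim analysis. There are two coherent choices.

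1. **FOPQ-C total score as sole primary.** This matches the existing power calculation. Make parent fear the first key secondary, tested only if FOPQ-C is significant, and make PHODA-YE secondary or supportive. Power stays at 87% and the sample size does not change.
2. **Keep parent fear as primary and require both.** State that FOPQ-C and the parent scale must both be significant. No alpha split is needed. Joint power is about 87% under the planned effects.

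Splitting alpha so that either could suffice is more expensive: at 0.025 each, adolescent power falls to 80.0% with 58 remaining, and to 70.4% with 52 remaining and a difference of 16.6.

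State in section 9.4 that the stopping rules apply to FOPQ-C, or to both measures if both are required. Use one name for the parent scale. The definition should also name its time point, since the hypothesis starts at discharge while power is given for 3 and 6 months.

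The change is wording only and needs no new data. The cost is that parent fear either loses its primary label, as section 9.2 already implies, or becomes a joint requirement.

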9.5.2 Secondary Outcomes

The secondary outcome is disability. This will be measured with the Functional Disability Inventory (FDI) measure at Baseline, treatment study Discharge, and 3 and 6-month post-discharge follow-up time points.

9.5.3 Additional Outcomes

Additional outcomes of interest include parent responses to pain and school functioning. These will be collected at Baseline, treatment study Discharge and 3 and 6-month post-discharge follow-up time points with the following measures: Adult responses to Child's Symptoms (ARCS), Helping for Health Inventory (HHI), Parent Psychological Flexibility Questionnaire (PPFQ), Chronic Pain Questionnaire (PPAQ), and Pediatric Quality of Life – School Functioning Subscale (PedsQL).

9.5.4 Exploratory Outcomes

Physical Activity (Actigraphy), Daily Diary (Child and Parent), and Biomechanics (motion analysis) are exploratory outcomes. Actigraphy will be measured during 2-week pre-treatment baseline throughout active treatment. The Daily Diary will be administered for an average of 14 days during the initial baseline period through treatment, and again for 7 days at the 3 and 6-month follow-up time points. Motion analysis will be conducted at Baseline and Discharge sessions.

9.5.5 Feasibility Measures

Feasibility will be measured in terms of treatment satisfaction, acceptability, adherence, fidelity, and healthcare use/cost. Treatment satisfaction will be evaluated by mean satisfaction of the Pain Service Satisfaction Test (PSST)⁶⁰ scores completed by child participants in both intervention groups. Treatment Acceptability will be measured by the Treatment Expectancy and Creditability measure (TEC-C, TEC-P)⁶¹, along with exit interviews collected at the discharge session. Adherence and Retention will be examined through mean parent and patient adherence to daily diary completion, percent of patient who drop out prior to treatment completion, and percent of sessions completed on schedule. A trained research assistant will listen to audio/video recordings of treatment sessions and complete treatment fidelity checklists for content and process, for both parents and child sessions (See Supplemental Materials I for checklists). Healthcare use/cost will be measured at the Baseline and 3 and 6-month follow-up time points with the Healthcare Cost Diary⁶².

Table 6. Assessment Measures

Outcomes & Correlates	Questionnaires & Tests	DD	Full version
Aim 1			
Primary Outcome			
Pain-related Fear Avoidance	Fear of Pain Questionnaire (FOPQ-C; PFOPQ) FOPQ-C: low [0-34] moderate [35-49] high [50-96]; Photographs of Daily Activities for Youth English (PHODA-YE)	x	BAS, END, FU3, FU6
Secondary Outcome			
Functional Disability	Functional Disability Inventory (FDI) mild [0-12] moderate [13-29] severe [30-60]	x	BAS, END, FU3, FU6
Additional Outcomes			
Protective Behaviors	Adult Responses to Child's Symptoms (ARCS), Helping for Health Inventory (HHI)	x	BAS, END, FU3, FU6
Parent Flexibility	Parent Psychological Flexibility Questionnaire (PPFQ-10)	x	BAS, END, FU3, FU6
Pain Acceptance	Chronic pain acceptance questionnaire (CPAQ-A; PPAQ)	x	BAS, END, FU3, FU6
School Functioning	Pediatric Quality of Life – School Functioning Subscale (PedsQL)		BAS, END, FU3, FU6
Exploratory Outcomes			
Biomechanics	Gait (stride length, velocity), vertical drop landing, dynamic postural control		BAS, END
Physical Activity	Daily mean and peak activity via Actigraphy	x	

Correlates			
Pain Severity	Numerical Rating Scale (NRS)	x	BAS, END, FU3, FU6
Pain Catastrophizing	Pain Catastrophizing Scale (PCS-C, PCS-P)		BAS, END, FU3, FU6
Medical History	Pain Questionnaire: Time since onset, previous treatments (Pain-C, Pain-P)		BAS
Demographics	Age, sex, socioeconomic status (Caregiver History)		BAS
Readiness to change	Pain Stages of Change Questionnaire (PSOCQ-A; PSOCQ-P)		BAS, END, FU3, FU6
Depression	Children's Depression Inventory-2 (CDI-2)		BAS, END, FU3, FU6
Anxiety	Multidimensional Anxiety Scale for Children (MASC)		BAS, END, FU3, FU6
Feasibility Measures			
Treatment Acceptability	Treatment satisfaction (PPST); mean score 40 of 60; satisfied to very satisfied		END, FU3, FU6
Treatment Acceptability	Treatment Expectancy & Credibility (TEC-C; TEC-P);		S1
Treatment Acceptability	% drop-out; Exit Interview (patient/parent feedback)		END
Treatment Adherence	% adherence to daily diary, at-home tasks, sessions completed on-schedule		END
Treatment Fidelity	Process (e.g., reflective listening), Content (session outline adherence)		**
Healthcare Use/Cost	Cost diary		BAS, WK, FU3, FU6

**To be assessed by ongoing coding of audio/video recordings of treatment sessions

BAS=Baseline, DD=Item Generation for Daily Diary; WK= Weekly during treatment, END=End of treatment, FU3=3-month follow-up, FU6=6 month follow-up, S=Session.

9.6 Data Analyses

Our statistician, [name], will conduct analyses. Linear mixed effects models will be used for Aim 1. We chose the largest feasible study size to obtain as precise estimates as possible of treatment difference in our primary outcome, adolescent pain-related fear. With a starting sample of 74 (37/37), we expect 58 at follow-up (18% discharge attrition, 5% at 3 and 6-month follow-up). Using GET Living pilot data (see Table 2), we used a mixed model simulation using the standard deviations at each time point and standard deviations of change to calculate correlation and hence the random effect and error variances. In our primary power calculation, we assumed that the improvement in adolescent pain-related fear at 3 and 6-months would be 22.4 in GET Living and 5 in TPM¹⁹, a difference of 17.4, with a standard deviation for change of 21. Under this scenario we will have 87% power with 58 (29 in each arm) at study end. Under more conservative assumptions, we still have power of 80% with only 52 at the end of study and a treatment difference

of 16.6. With a smaller standard deviation of 18.9, we will have power of 80% with 50 at end of study and a treatment difference of 15.4.

10. DATA COLLECTION AND QUALITY ASSURANCE

10.1 Data Collection Forms

REDCap (Research Electronic Data Capture), the free, secure, HIPAA compliant web-based application, will be used to collect, store, and manage data. Vanderbilt University, with collaboration from a consortium of academic and non-profit institutional partners, has developed this software toolset and workflow methodology for electronic collection and management of research and clinical study data. Data will be maintained in private, non-shared, protected folders stored on central computers at Stanford University School of Medicine. The hospital system provides nightly backup of files stored on its server. Only approved research staff will have access to these files. Identifying information will not be entered or stored on the computer with the behavioral data; thus, all relevant data other than separated consent forms will be de-identified. Documentations of clinical treatment sessions from the Screening and Treatment Delivery team will be collected weekly and stored in a study file for the participant by the study coordinator.

10.2 Data Management

All questionnaire data collected for the study will be exported into SPSS, SAS or R via REDCap. Databases for all data collected for the purposes of this research study will be stored in a password protected SPSS file which only research staff will have access. Datasets related to this clinical trial will only be accessed by [name] (PI) and research team as needed. The database will be stored on a password protected, secured and encrypted server maintained by [name] and Stanford University IT.

The Photographs of Daily Activity (PHODA) is a data collection platform that will be maintained by the study coordinator and administered to all patients at baseline and discharge sessions. Biomechanical data and analysis will be collected and maintained by the Motion and Sports Performance Laboratory (MSPL) at SCH and verified by the communications with the study coordinator on a weekly basis.

Actigraphy data will be collected using ActiLife software and maintained by the study coordinator.

Scheduling and enrollment data will be stored in an excel spreadsheet within a PHI-safe folder on Stanford Medicine Box – a secure, HIPAA compliant cloud-based data storage platform.

Treatment session audio/video recordings will be collected digitally and saved on the secure, private drive on the server and only personnel associated with the study will have access to the files. After completion of the study, all audio and video recordings will be destroyed.

